**Table 2: Timing Window Allowances for PK/PD Sampling, ECG, and Vital Sign Measurements**

Pharmacokinetic and Pharmacodynamic Sampling	
Timepoint	Tolerance Window
0 hour	-240 min to 0 hour
5 minutes post end-of-infusion	± 5 minutes
2, 4, & 6 hours post end-of-infusion	± 15 minutes
24 hours post end-of-infusion	± 60 minutes
48 hours post end-of-infusion	± 120 minutes
ECG	
Timepoint	Tolerance Window
5 minutes post end-of-infusion	± 10 minutes
Vital Signsa	
Timepoint	Tolerance Window
0 hour	-240 min to 0 hour
15, 30, and 45 minutes after start of infusion	± 5 minutes
60 minutes after start of infusion	± 10 minutes
30, 60 and 120 minutes post end-of-infusion	± 10 minutes

a: Vital signs to include blood pressure, pulse rate, respiratory rate, oral temperature, and pulse oximetry.

---

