- b: **Vital sign** measurements (sitting blood pressure, heart rate, respiratory rate, and oral temperature) to be obtained after 5 minutes of seated rest. Any abnormal measurements are to be repeated after 5 minutes of rest. On Days 0, 7, 14, 21, and 28 vital sign measurements will be collected immediately prior to the infusion; 15, 30, and 45 minutes after the start of the infusion; at completion of the infusion; and 30 minutes, 1 hour and 2 hours following completion of the infusion.
- c: **Pulse oximetry**: On Days 0, 7, 14, 21, and 28, pulse oximetry to be measured immediately prior to the infusion; 15, 30, and 45 minutes after the start of the infusion; at completion of the infusion; and 30 minutes, 1 hour and 2 hours following completion of the infusion.
- d: **Clinical safety labs**: hematology, clinical chemistry, and urinalysis (see [Section 6.7](#) for a complete list). Full clinical safety lab draws will be collected at Screening and on Days 0, 7, 14, 21, 28, 33, 42, 56, 84 and 112.
- e: **Pregnancy test**: To be performed at time of screening and prior to first dose of SYNT001 on Day 0 and on Days 56 and 112 (urine or serum test is acceptable, however, positive urine tests must be confirmed with serum testing.)
- f: Digital 12-lead **ECG** to be obtained after 5 minutes of rest in the supine position and in triplicate at least 1-2 minutes apart (see [Section 6.6](#) for additional information). On Days 0 and 28 to be obtained 5 minutes after the completion of infusion. Day 12 ECG will be collected only if the visit is conducted at the study site.
- g: **Serology**: Testing at Day 56 will not be done for any subject whose baseline titer is below the level of detection. If the Day 56 results are greater than 30% below the baseline value, or if the subject falls below the level of detection, the subject will be re-tested at Day 84; if still below the baseline value (or level of detection), the subject will be re-tested at Day 112. Any subject whose baseline value for tetanus or VZV was above the detectable level at baseline, and is not within 30% of the baseline value or is below the detectable level by Day 112, will be referred to their primary care physician for further management. See [Section 6.7.3](#) for additional information.

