### 4.2 Study Endpoints

**Primary Outcome Measures:** Assessment of safety data (adverse events [AEs], serious adverse events [SAEs], vital sign measurements, ECGs and clinical laboratory tests) will be the primary safety measure.

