## 6.5 Vital Sign Measurements

Vital sign measurements will be collected after the subject has been sitting for 5 minutes. Vital sign assessments will include measurements of sitting blood pressure (mm Hg), heart rate (beats per minute), respiration rate (breaths per minute), oral temperature (Celsius). Abnormal results are to be repeated after 5 minutes of rest. Pulse oximetry (%) also is to be measured. See [Table 2](#) for timing window allowances with respect to measurement collection.

On Days 0, 7, 14, 21, and 28, vital sign measurements are to be obtained immediately prior to the infusion; 15, 30, and 45 minutes after the start of the infusion; at completion of the infusion; and 30 minutes, 1 hour and 2 hours following completion of the infusion. Details on the management of mild to moderate and severe infusion reactions can be found in [Figure 1](#) and [Figure 2](#). Abnormalities in vital sign measurements will be graded in severity per the NCI CTCAE scale Version 4.03.

Subjects should be seated quietly for at least 5 minutes in a chair with their backs supported, their feet flat on floor (legs uncrossed), and their arms bared on a hard surface, with the arm slightly abducted and bent, with palm up and the midpoint of upper arm at heart level. Correct cuff and bladder size should be utilized and the same cuff and arm should be used per subject throughout study.

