## 6.6 12-Lead Electrocardiogram (ECG)

Digital 12-lead ECG measurements will be obtained at screening, on Days 0 and 28 at 5 minutes after the completion of the infusion and at the Day 56 visit. Subjects who conduct their Day 12 visit at the investigative site, as opposed to an at-home nurse visit, will have an additional ECG performed. ECGs are to be performed with the subject in a supine position having rested in this position for at least 5 minutes before each reading. ECGs are to be performed in triplicate, each 1 to 2 minutes apart. See [Table 2](#) for timing window allowances with respect to performing ECG.

The following ECG parameters will be collected: PR interval, QRS interval, and QT interval. The ECG findings will be evaluated by a qualified physician for the presence of abnormalities (qualitative assessment). The physician will assess each ECG as normal, abnormal/not clinically significant, or abnormal/clinically significant.

Normal QTcF is  $\leq 450$  msec.

Abnormalities in the ECG that appear following therapy or that result in clinical signs and symptoms are considered clinically significant for the purposes of this study and will be recorded on the AE eCRF.

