### **Guidelines for Grading and Management of Allergic or Infusion-Related Reactions**

Allergic and/or infusion-related reactions include hypersensitivity reactions and cytokine release syndromes. These reactions are experienced by patients during or within hours of the infusion of monoclonal antibody therapy. Symptoms can include flushing, alterations in heart rate and blood pressure, dyspnea, bronchospasm, back pain, fever, urticaria, edema, nausea, and all types of rashes. Anaphylaxis is recognized as a severe, life-threatening, generalized, or systemic reaction. This is a medical emergency characterized by rapidly developing life-threatening airway and/or breathing and/or circulation problems usually associated with skin or mucosal changes.

[figure not shown]
Management of Grade 1 infusion reactions include interrupting the infusion or decreasing the rate of infusion by 50% and observing. Symptoms may also be treated as needed with medications such as diphenhydramine, hydrocortisone or acetaminophen, either alone or in combination, depending on the subject's signs and symptoms. If the infusion is interrupted or the infusion rate is decreased, it is important to note that all study drug infusions must be completed within 4 hours of SYNT001 administration.

Management of Grade 2 and higher infusion reactions should include stopping the infusion of study drug. See [Figure 1](#) and [Figure 2](#) for details on the management of Grade 2 and Grade 3 or higher infusion reactions. The severity of and management of allergic or infusion-related reactions will be graded and managed using NCI CTCAE Version 4.03 (see [Table 5](#)).

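### Table 2's tolerances do not fit the times they serve: the completion vital signs are timed from infusion start, the post-infusion ECG window opens before the infusion ends, and pre-infusion vital signs may be four hours old

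*Protocol*

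**What the plan says.** **Nominal times.** On Days 0, 7, 14, 21 and 28, Section 6.5 says that "vital sign measurements are to be obtained immediately prior to the infusion", then at 15, 30 and 45 minutes after the start, and then "at completion of the infusion; and 30 minutes, 1 hour and 2 hours following completion of the infusion". Table 1 footnote b repeats that "vital sign measurements will be collected immediately prior to the infusion", footnote c gives the same times for pulse oximetry, and the dosing-day lists in Section 7 agree. Section 6.6 schedules the ECG "on Days 0 and 28 at 5 minutes after the completion of the infusion". Sections 7.2 and 7.11 list that ECG among the procedures that follow drug administration.

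**Tolerances.** Sections 6.5 and 6.6 both refer to Table 2. Its vital-sign block, which a footnote extends to pulse oximetry, gives:
- 0 hour: "240 min to 0 hour", with a minus sign before the 240;
- 15, 30 and 45 minutes after start: ±5 minutes;
- "60 minutes after start of infusion": ±10 minutes;
- 30, 60 and 120 minutes after infusion end: ±10 minutes.

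There is no row for completion. The ECG is set at 5 minutes after infusion end, ±10 minutes. The PK sample at the same nominal time has ±5 minutes.

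**Infusion length.** The infusion is planned over 1 hour. For a Grade 1 infusion reaction, Section 9.6.1 provides for "interrupting the infusion or decreasing the rate of infusion by 50% and observing", with completion required within 4 hours.

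**The concern.** A tolerance should allow for small delays around a nominal time without changing what the reading means. Three cells of Table 2 do change it.

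The completion reading is anchored to the wrong end of the infusion. When the infusion runs long, a site that follows the row exactly records a mid-infusion value. This falls on subjects whose infusion was slowed or interrupted, often because they reacted, and theirs are the end-of-infusion readings of most interest.

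The ECG window admits a tracing taken while drug is still running, although the ECG is scheduled as post-infusion. Days 0 and 28 have the only ECGs tied to infusion end.

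The 0-hour window admits a pre-infusion value much older than Section 6.5 suggests.

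Section 4.2 says that the safety data ("vital sign measurements, ECGs and clinical laboratory tests) will be the primary safety measure") include these measurements. Section 12.5 summarises vital signs and ECG parameters, with change from baseline, by time point. At stake is whether those time points mean the same thing across subjects and about 10 sites. No error rate or sample size is involved.

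**Working it through.** The protocol gives no figure of its own to reproduce. The check is interval arithmetic on the Table 2 windows.

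**1. Completion vital signs and pulse oximetry.** The window is 60 ± 10, so 50 to 70 minutes after start.

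- Uninterrupted infusion: it ends at 60, so the window runs from 50 − 60 = −10 to 70 − 60 = +10 minutes around completion. The row works.
- Rate halved at 30 minutes and kept there: half the volume is in at 30 minutes, and the other half takes 30 × 2 = 60 minutes. Completion is at 30 + 60 = 90. The window runs from 50 − 90 = −40 to 70 − 90 = −20, so it closes 20 minutes before completion.
- Half rate for the first 30 minutes, then full rate, as the August 2017 clarification letter describes for infusions after a reaction (the current Figure 1 is not shown): 25% is in at 30 minutes, and the remaining 75% takes 0.75 × 60 = 45 minutes. Completion is at 75, and the window runs from −25 to −5.
- General case, halved at minute t and kept there: completion = t + 2 × (60 − t) = 120 − t. This lies within the window only if 120 − t ≤ 70, that is t ≥ 50.
- Interruption of p minutes, resumed at full rate: completion = 60 + p, outside the window once p exceeds 10.

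**2. ECG.** The window is 5 − 10 = −5 to 5 + 10 = +15 minutes around infusion end. The PK sample at the same nominal time has 5 − 5 = 0 to 5 + 5 = +10, so it cannot precede the end. Section 6.6 spaces the three ECG readings 1 to 2 minutes apart, so a triplicate spans 2 to 4 minutes. One started at −5 finishes between −3 and −1, wholly before infusion end and still within the window.

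**3. Pre-infusion vital signs.** The oldest admissible value is 240 / 60 = 4 hours before start, or 240 / 60 = 4 times the planned infusion length. Every other vital-sign row is held to ±5 or ±10 minutes.

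**Weight in the summaries.** With 8 subjects per cohort, one mis-timed value is 1/8 = 12.5% of a cohort mean at that time point.

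**The case against.** The strongest reply is that tolerances are not contradictions. Sections 6.5 and 6.6 set nominal times and expressly defer to Table 2, so a reader who infers that no site can satisfy both goes too far. That is right. The fault is poor fit, and it differs by row.

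- **Completion row.** Table 2 is written for a 60-minute infusion, where the row is correct at its nominal time. For a slowed infusion, Section 6.5 and the visit lists still ask for a completion reading, so Table 2 does not abolish it. Both points stand. But a completion reading taken on time then has no matching Table 2 row, and a reading taken by the row is early.
- **Size.** A reader might take half rate throughout, ending at 120 minutes, as the natural case. The documents do not describe that course, so it should not be used. The clarification letter also reports no infusion reactions and no slowed or interrupted infusions in the Phase 1a study, so frequency here is unknown.
- **ECG.** Sections 7.2 and 7.11 already place it after administration, and at −5 minutes 55/60 = 92% of a planned infusion is in. The effect on interpretation is therefore probably small. The window still permits what those sections exclude.
- **0-hour window.** Five minutes of seated rest and morning dosing limit the extra variation. The PK pre-dose sample is described in similarly close terms and has the same 240-minute allowance. This is the weakest of the three parts.
- **Consequences.** It would be tempting to say that infusion reactions will be missed, or that the primary analysis is compromised. The 15, 30 and 45-minute rows agree with Section 6.5. The synopsis lists only AEs and laboratory tests as the primary endpoint. How readings map to analysis time points may be settled in the SAP, which is not shown.

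**Conclusion.** The point holds as a mismatch between Table 2's tolerances and the times they serve, with modest impact. The completion row is sound only for an infusion that is uninterrupted or nearly so. For a rate halved at 30 minutes, its window closes 20 minutes early. The ECG window wrongly admits the last 5 minutes of infusion. The 4-hour pre-infusion allowance sits badly with Section 6.5 but is the least consequential of the three.

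The completion figures assume a constant planned rate over 60 minutes and a reduction that is either maintained or reversed as stated. The ECG figure assumes that the window applies to the triplicate as written. How many subjects would be affected cannot be derived from the documents. Because the analyses are descriptive and the cohorts have 8 subjects, the matter is one of clean, comparable safety time points. It does not show that any safety conclusion would be wrong. It is still worth correcting, since collection times cannot be repaired once the data are in.

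**What to change.** Reconcile Table 2 with Sections 6.5, 6.6 and 7 in three cells:

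1. Anchor the completion vital-sign and pulse-oximetry row to the actual end of infusion instead of a fixed time from the start.
2. Start the ECG window no earlier than the end of infusion.
3. Align the 0-hour vital-sign window with the close timing in Section 6.5, separately from the window for blood samples.

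The sponsor should choose the window lengths, as the documents give no basis for particular values. Nothing here changes how the infusion is given or how reactions are managed.

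The cost is three table cells, a memo to sites and an edit to the data-capture windows, with no new procedure. The downside is slightly tighter scheduling on the dosing days.

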## LIST OF ABBREVIATIONS

ADA	Anti-drug antibodies
AE	Adverse event
AECA	Anti-epithelial cell antibody
ALT	Alanine aminotransferase
ANA	Antinuclear antibody
AST	Aspartate aminotransferase
ATC	Anatomical therapeutic chemical
AUC 0-24	Area under the plasma concentration-time curve from pre-dose (time 0) to 24 hours post-dose
AUC 0-∞	Area under the plasma concentration-time curve from pre-dose (time 0) to infinity
BLQ	Below the limit of quantification
BMI	Body mass index
BUN	Blood urea nitrogen
CAR-T	Chimeric antigen receptor and T-cell
CFR	Code of Federal Regulations
C3	Complement component 3
CBC	Complete blood count
CIC	Circulating immune complexes
CIDP	Chronic inflammatory demyelinating polyneuropathy
C max	Maximum plasma concentration determined directly from the concentration-time profile
CRO	Contract research organization
CV	Coefficient of variation
CVID	Common variable immune deficiency
DEC	Dose escalation committee
D5W	Dextrose 5% in Water
DIF	Direct immunofluorescence
DNA	Deoxyribonucleic acid
ECG	Electrocardiogram
eCRF	Electronic case report form
ESR	Erythrocyte sedimentation rate
FcGR2a	Fc Gamma R2a receptor
FcRn	Neonatal Fc receptor
FDA	Food and Drug Administration
GCP	Good Clinical Practice
GI	Gastrointestinal
HBV	Hepatitis B virus
HCV	Hepatitis C virus
HIPAA	Health Insurance Portability and Accountability Act
HIV	Human immunodeficiency virus
IB	Investigator's brochure
IC	Immune complex

---

ICF	Informed consent form
ICH	International Conference on Harmonization
IgA	Immunoglobulin A
IgG	Immunoglobulin G
IgG1-4	Immunoglobulin G1-G4
IgM	Immunoglobulin M
IL-12	Interleukin 12
IND	Investigational new drug
IRB	Institutional review board
ITT	Intent-to-treat
IUD	Intrauterine devices
IV	Intravenous
IVIG	Intravenous immunoglobulin
MedDRA	Medical Dictionary for Regulatory Activities
NHL	Non-Hodgkin lymphoma
PD	Pharmacodynamics
PE	Physical examination
PK	Pharmacokinetic
RBC	Red blood cells
RNAseq	RNA sequencing
QTcF	Corrected QT interval using Fridericia's formula
SAE	Serious adverse event
SAP	Statistical analysis plan
SAS	Statistical Analysis System
SD	Standard deviation
SNP	Single nucleotide polymorphism
SOC	System Organ Class
SOP	Standard operating procedures
SYNT001	A humanized, affinity matured IgG4-kappa monoclonal antibody
$t_{1/2}$	Half-life
TEAE	Treatment-emergent adverse event
$T_{max}$	Observed time to reach peak plasma concentration
TNF	Tumor necrosis factor
ULN	Upper limit of normal
UNS	Unscheduled
VZV	Varicella-zoster virus
WAIHA	Warm antibody autoimmune hemolytic anemia
WHO	World Health Organization
WHO-DD	World Health Organization Drug Dictionary

---

## 2 BACKGROUND AND RATIONALE

SYNT001, a humanized, affinity-matured IgG4-kappa monoclonal antibody (mAb), blocks IgG and IgG immune complex (IC) interactions with the neonatal Fc receptor (FcRn) and thereby the major functions of FcRn in protecting IgG and IgG ICs from degradation and their role in downstream signaling events. Specific and high affinity blockade of FcRn with SYNT001 has been shown to increase the catabolism of IgG and IgG IC in healthy volunteers. This predicts that SYNT001 will also accelerate degradation of endogenous circulating IgG autoantibodies and IgG-antigen IC specifically involved in the pathogenesis of autoimmunity. Blocking FcRn interactions with IgG-containing ICs further predicts that SYNT001 will have consequences for innate and adaptive cellular immunity. In the first instance, blocking multimeric IgG IC interactions with FcRn within antigen-presenting cells will result in inhibition of IC-stimulated inflammatory cytokine production and release by these cells. In addition, as FcRn determines the intracellular itinerary of IgG ICs within and among compartments important in cellular immunity, it is anticipated that SYNT001 will block antigen processing and presentation of antigens contained within IC that otherwise lead to CD8+ and CD4+ T cell activation. Thus, SYNT001 will specifically target immune functions associated with IgG that are involved in certain autoimmune conditions and dismantle their ability to cause disease.

SYNT001 targets key mechanisms contributing to pathology in a variety of IgG-mediated autoimmune disorders, including warm antibody autoimmune hemolytic anemia (WAIHA), pemphigus, and chronic inflammatory demyelinating polyneuropathy (CIDP).

While current treatments for certain autoimmune disorders, including high-dose steroids, immunosuppressants, intravenous immunoglobulin (IVIG), plasmapheresis, and anti-CD20 monoclonal antibodies (mAbs), such as rituximab, can be effective, they are associated with significant adverse effects, as well as delayed or non-durable responses.

Pemphigus is a rare group of blistering autoimmune diseases that affect the skin and mucous membranes. Autoantibodies have been shown to play an important pathogenic role in the mucosal and cutaneous manifestations in patients with pemphigus. Administration of SYNT001, which significantly decreases total IgG, including a corresponding decrease in the level of the pathogenic autoantibodies and the ICs to which they are associated, may lead to a decrease in the mucosal and cutaneous manifestations in patients with pemphigus. Moreover, the ability of SYNT001 to reduce circulating immune complexes (CICs) and the associated innate and adaptive immune responses may allow for further sustained disease modification.

---

## 2.1 Study Rationale

This study is being conducted to evaluate the safety, tolerability, pharmacokinetics (PK), pharmacodynamics (PD) and immunogenicity of intravenous (IV) SYNT001 as well as its effects on pemphigus disease activity markers.

## 2.2 Selection of Doses in this Study

The planned dose levels of SYNT001 for this Phase 1b safety and proof-of-concept study of 10 mg/kg and 30 mg/kg were selected from careful review of the safety, tolerability, and PD effect on total IgG levels after single and repeat dosing of SYNT001 in non-human primates (NHPs), as well as the safety, tolerability, and PD effect on total IgG levels after single ascending doses of SYNT001 in healthy volunteers. In addition, further consideration was given to the desired level of FcRn blockade to achieve suppression of IgG to a range that has been previously correlated with disease remission. Further, we considered the potential effects of inhibiting FcRn function as they relate to immune complex associated innate and adaptive immunity in choosing these dose levels based upon exploratory studies of a single ascending dose of SYNT001 in healthy volunteers. From the NHP studies, single doses of SYNT001 produced a dose-dependent decrease in total IgG and a further decrease was seen with repeated weekly doses up to a maximum 70% reduction at 100 mg/kg. This magnitude of total IgG reduction is approaching the expected maximal effect of 100% inhibition of FcRn function based on murine studies also performed by Syntimmune and others (Nixon et al., 2015; Roopenian et al., 2003). In the recently completed Phase 1a trial with SYNT001 in healthy volunteers a single dose caused a maximum average 50% drop in total IgG with IV dosing at 30 mg/kg. Based on the NHP studies further reductions are expected following multiple dosing. A comparable decrease in pathogenic autoantibodies is also anticipated.

In the NHP studies, relevant adverse effects, mild-to-moderate infusion reactions, were observed only after the third weekly IV administration, concurrent with the development of anti-SYNT001 antibodies. In the recently completed Phase 1a healthy male volunteer study, the doses of SYNT001 up to and including 30 mg/kg have been well tolerated. There were no dose limiting toxicities, serious adverse events, or any other safety concerns identified. No AEs were observed in the 1 and 3 mg/kg dose cohorts. A single Grade 2 AE was observed; a headache in the 10 mg/kg cohort. Other subjects had mild (Grade 1) AEs at 10 mg/kg. In Cohort 4 (30 mg/kg), 5 subjects received SYNT001. All five subjects experienced AEs; all were mild (Grade 1), transient and resolved spontaneously without intervention. Therefore, it is anticipated that the doses selected for this study should be well tolerated and have clinically relevant PD effects in patients with chronic pemphigus (vulgaris or foliaceus). For a summary of findings from the

single dose, clinical study in healthy subjects and further details on the nonclinical findings, please refer to the SYNT001 Investigator's Brochure.

